### **5.2 Adjustments for Covariates**

No adjustments for covariates will be made.

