9.7 Study Follow Up

Study-related follow-up visits occur at the investigational site at, 72 Hours (Visit 4) Post-TKA as well as Week 2 (Visit 5), Week 6 (Visit 6), and Week 12 (Visit 7) Post-TKA. The study's schedule of assessments is shown in Table 2.

Follow Up Visit 4 (72 hours \pm 24 hours post op) - Phone Call

Visit 4 (72 Hours Post-TKA) will occur via a phone follow-up. No physical performance measures will be collected at these visits. Subjects will self-report the amount of opioids used. Subjects will report the NRS Pain Scores, answer the KOOS Jr. questions and report any AEs if present.

[figure not shown]
Follow Up Visit 5 (2 Weeks; \pm 3 Days Post Op), and Visit 6 / 6 Weeks Post-op (6 weeks; \pm 5 Days Post-Op)

Subjects will be evaluated and data collected per the schedule of events. Any changes in concomitant medications/concurrent procedures will be documented. Any anticipated observations, adverse events, adverse device effects and/or SAE/UADE/USADE will be assessed and documented. Photographs may be taken of the treatment area.

The Subject will complete a KOOS JR. questionnaire and NRS for Pain when standing from a seated position for all follow-up visits. The Subject will also complete a [REDACTED] [REDACTED] will answer Satisfaction questions at Visit 6.

The subject will complete the Physical Performance Measures for Visit 5, 6 and 7 in the following order under supervision of the investigator or designee:

- ! [REDACTED]
- Time Get-Up and Go

Subjects will be asked to bring all prescription opioid bottles to all study follow-up visits. A pill count will be completed by the study coordinator, or designee, and opioid medication will be returned to subjects.

Follow Up Visit 7 (12 Weeks; \pm 7 days Post-Op)

Subjects will be evaluated and data collected per the schedule of events. Any changes in concomitant medications/concurrent procedures will be documented. Any anticipated

observations, adverse events, adverse device effects and/or SAE/UADE/USADE will be assessed and documented. Photographs may be taken of the treatment area.

The Subject will complete a KOOS Jr. questionnaire, NRS for Pain when standing from a seated position. The Subject will also complete a [REDACTED] will answer Satisfaction questions.

The subject will complete the Physical Performance Measures in the following order under supervision of the investigator or designee:

- Get up and Go Test

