### 3.2 Method of Assigning Subjects to Treatment

After meeting all of the inclusion and none of the exclusion criteria and prior to study treatment, subjects will be randomized in a 1:1 manner to either:

- **iovera° Treatment:** Subject undergoes treatment with the study device using study supplied Smart Tip.
- **Standard of Care Treatment:** Subject does not undergo iovera° Treatment

The Investigator or designee will record the randomization assignment in the source documentation and CRF.

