### **4.2 Secondary Effectiveness Endpoints**

The secondary effectiveness endpoints are as follows:

1. AUC/time (see definition of AUC/time below) based on Changes from Baseline in KOOS JR. Scores through 6 weeks post-TKA
2. AUC/time based on Changes from Baseline through 6 weeks post-TKA in NRS for Pain
3. AUC/time based on Changes from Baseline through 6 weeks post-TKA in Timed Get Up and Go (TUG) test

Change in KOOS JR. scores from the Baseline visit to each post-baseline visit will be calculated for each subject as:

Change in KOOS JR. score =

Post-Baseline Visit KOOS JR. score – Baseline Visit KOOS JR. score,

such that a positive value indicates an increase in the KOOS JR. score, which is a positive outcome, while a negative value indicates a decrease, which is a negative outcome. Change in NRS for Pain scores from the Baseline visit to each post-baseline visit will be calculated for each subject as:

Change in NRS for Pain score =

Baseline Visit NRS for Pain score – Post-Baseline Visit NRS for Pain score,

such that a positive value indicates a decrease in the NRS for Pain score, which is a positive outcome, while a negative value indicates an increase, which is a negative outcome. Change from baseline in the TUG test is defined analogously to the change from baseline in NRS for Pain score. The first and key secondary effectiveness endpoint, AUC/time based on Changes from Baseline in KOOS JR. scores through 6 weeks post-TKA, is the area under the curve (AUC) of Change in KOOS JR. scores from the Baseline visit through the 6-week visit divided by the number of days from TKA until the 6-week visit. AUC will be calculated using the trapezoidal rule and the changes in the KOOS JR. score at the following time points: Baseline (change=0), 72 hours, 2 weeks, and 6 weeks post-TKA. The second and third secondary effectiveness endpoints are defined analogously.

[REDACTED]

[REDACTED]

[REDACTED]

[REDACTED]

- [REDACTED]
- [REDACTED]
- [REDACTED]

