### **5.3 Handling of Dropouts and Missing Data**

Missing data for the primary effectiveness endpoint and the first secondary effectiveness endpoint will be imputed using multiple imputation methods. First, the relatively uncommon, non-monotone missing data will be imputed using the MCMC option of SAS® PROC MI. For example, for the primary effectiveness endpoint, the imputation model will include a term for treatment and the pill counts at visits 4, 5, and 6. Second, the monotone missing values will be imputed using the chained equation method by SAS® PROC MI option MONOTONE REG. For each subject within each imputed dataset, the value of the endpoint will then be determined. The imputed data sets will each be analyzed as specified in Sections 8.1 and 8.2, and the results will be summarized using PROC MIANALYZE.

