## **5.8 Baseline**

Baseline will be defined as the value at the Screening visit. If the value for an assessment is missing at Screening and there is an unscheduled assessment prior to treatment, the value from the unscheduled assessment will be used as the baseline value.

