Let  $\mu_{2,\text{Active}}$  and  $\mu_{2,\text{SOC}}$  denote the true mean AUC/time based on the Change from Baseline in KOOS JR. score from the Baseline visit through the six-week visit for the active and standard of care treatments, respectively. Then the null and alternative hypotheses for the test for non-inferiority for this endpoint are as follows:

$$H_0: \mu_{2,\text{SOC}} - \mu_{2,\text{Active}} \geq \delta$$

$$H_1: \mu_{2,SOC} - \mu_{2,Active} < \delta,$$

where the non-inferiority margin  $\delta=14$ .

Missing KOOS JR. data will be imputed using multiple imputation methods. First, the relatively uncommon, non-monotone missing data will be imputed using the MCMC option of SAS® PROC MI. The imputation model will include a term for treatment and the KOOS JR. score at visits 1, 4, 5, and 6. Second, the monotone missing values will be imputed using the chained equation method by SAS® PROC MI option MONOTONE REG. For each subject within each imputed dataset, the value of the endpoint will then be determined. The imputed data sets will each be analyzed to obtain the difference in means between treatments and the corresponding standard error, and the results will be summarized using PROC MIANALYZE (with THETA0=14, the non-inferiority margin, in the PROC MIANALYZE statement). The null hypothesis will be tested using a one-sided t-test. One of the secondary objectives of the study is to show that, over the 6-week post-TKA period, the Active Treatment group has similar levels of pain and functioning as compared to the Standard of Care Treatment group. This objective will be met if the t-test for non-inferiority is statistically significant using a 0.025 level of statistical significance.

There is one item in the KOOS JR. scale (Knee Twisting/Pivoting) with a large number of missing responses. Prior to undergoing multiple imputation, missing values for this item will be imputed by performing a linear regression (SAS PROC GLM) on the other 6 KOOS JR. items and imputing the Knee Twisting/Pivoting score for each patient with a missing value based on the estimated linear regression line. At baseline this imputation will be performed across treatment arms; at post-baseline time points the imputation will be performed by treatment arm.

Change in NRS for Pain scores and TUG test scores from the Baseline visit to each post-baseline visit will be calculated for each subject as:

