$$\text{Change score} = \text{Baseline Visit score} - \text{Post-Baseline Visit score},$$

such that a positive value indicates a decrease in the score (which is a positive outcome), while a negative value indicates an increase (which is a negative outcome). AUC/time for these endpoints will be calculated in the same way described above for KOOS JR.

Each secondary effectiveness endpoint will be summarized by treatment using descriptive statistics. For each treatment, the null hypothesis that the true mean AUC/time equals zero will be tested using a paired t-test. Ninety-five percent confidence intervals based on the t-distribution for the true mean AUC/time for each treatment and for the true difference in these means between treatments will be provided. For the second and third secondary effectiveness endpoints, a one-sided, two-sample t-test will be used to test the null hypothesis that the iovera mean is less than or equal to the Standard of Care mean versus the alternative hypothesis that the iovera mean is greater than the Standard of Care mean. In addition, for each secondary effectiveness endpoint, the initial result (e.g., KOOS JR. score at 6-weeks post-TKA), as well as the Change from Baseline value, will be summarized by treatment group at each visit at which data for the endpoint are collected using descriptive statistics, together with 95% confidence intervals for the mean based on the t-distribution. The estimated difference in the mean change from baseline between the two treatment groups and a 95% confidence interval based on the t-distribution for the true difference in these means between the two treatments will also be provided.

The fixed sequential testing procedure will be used for the comparison of the two treatments with respect to the first (and key) secondary effectiveness endpoint. Therefore, for this endpoint, the analysis comparing the two treatments will be formally conducted only if the analysis for the primary effectiveness endpoint yields a statistically significant result. For informational purposes, however, the results of the analyses (i.e., p-value) will be presented regardless of the results for the primary effectiveness endpoint.

These analyses will be performed for the ITT Population.

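### The secondary AUC/time tests leave out the Screening value as a covariate; they are valid, but usually less precise than ANCOVA would be

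*SAP*

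**What the plan says.** SAP 5.2 is a single sentence: "No adjustments for covariates will be made". SAP 8.2 follows it. For KOOS JR., the difference in mean AUC/time and its standard error are taken from each imputed dataset and combined, and "The null hypothesis will be tested using a one-sided t-test" against a margin of 14 at the 0.025 level. For NRS and TUG the text reads "For the second and third secondary effectiveness endpoints, a one-sided, two-sample t-test will be used to test the null hypothesis" of no superiority.

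All three endpoints are built from change from Baseline, which SAP 5.8 sets as the Screening value. SAP 4.2 says "AUC will be calculated using the trapezoidal rule and the changes in the KOOS JR. score at the following time points": Baseline (with change set to zero), 72 hours, 2 weeks and 6 weeks. The other two endpoints are defined in the same way. TUG has no 72-hour value, because Protocol 9.7 makes that contact a telephone call and says "No physical performance measures will be collected at these visits".

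The KOOS JR. Screening score enters the imputation model in SAP 8.2, but no analysis model contains it. On imputation, SAP 5.3 says "Missing data for the primary effectiveness endpoint and the first secondary effectiveness endpoint will be imputed using multiple imputation methods"; NRS and TUG are not covered.

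**The concern.** Subtracting baseline is not the same as adjusting for it. A change score fixes the coefficient of the baseline value in advance, while ANCOVA estimates it. Unless the fixed value happens to match the true regression slope, the unadjusted comparison carries variance that the Screening value could have removed.

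This matters most for KOOS JR. The trial aims to show less opioid use with similar pain and function, and the KOOS JR. test carries the second half of that claim. Neither document gives a power calculation for it; the sample size rests on opioid consumption alone. NRS and TUG lie outside the fixed testing sequence, so for them only the width of the interval is at stake. The primary endpoint has no defined baseline value and is not affected.

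**Working it through.** **The plan's own figure.** The only sizing figure is 57 per group for the primary endpoint. With the SAP 3.4 inputs (difference 12.0 mg, SDs 18.2 and 26.0 mg, one-sided 0.025), a Satterthwaite t-test has 80.7% power at 57 per group, which agrees with the stated aim of at least 80%. Nothing comparable exists for KOOS JR., NRS or TUG.

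**Baseline coefficient.** Use nominal visit days (SAP 5.9), divide by 42 days, and assume Baseline sits at Day 0. The trapezoidal weights on the follow-up values are:

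- KOOS JR. and NRS (days 0, 3, 14, 42): 7/42, 19.5/42 and 14/42; sum c = 40.5/42 = 0.964.
- TUG (days 0, 14, 42): 21/42 and 14/42; sum c = 35/42 = 0.833.

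So AUC/time = A − c × baseline, where A is the weighted sum of follow-up values (signs reversed for NRS and TUG). The SAP does not say where Baseline sits on the time axis. At the actual Screening day (−30 to −1), c would be 0.976 to 1.321 for KOOS JR. and NRS, and 0.845 to 1.190 for TUG. The argument below holds for any fixed c.

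**Variance comparison.** Set the baseline variance to 1. Let k be the ratio of post-operative to baseline SD, ρ the correlation of each follow-up value with baseline, and b = Cov(A, baseline) = ρkc. Then:

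- Var(change score) = Var(A) + c² − 2cb
- Var(ANCOVA) = Var(A) − b², times 1 + 1/110 for the extra parameter (N = 114)
- Before that factor, the difference is (c − b)², which is never negative and is zero only when b = c.

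Example for KOOS JR. with inter-visit correlation 0.5, k = 1.5 and ρ = 0.3. The squared weights sum to 0.3545 and c² = 0.9298, so Var(A) = 2.25 × (0.5 × 0.9298 + 0.5 × 0.3545) = 1.445. With b = 0.3 × 1.5 × 0.9643 = 0.434, Var(change) = 1.445 + 0.930 − 0.837 = 1.538 and Var(ANCOVA) = 1.445 − 0.188 = 1.257. The ratio is 0.817, or 0.825 with the factor.

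Variance ratios for inter-visit correlation 0.5 and ρ from 0.1 to 0.7 (all assumed):

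| SD ratio k | KOOS JR., NRS | TUG |
|---|---|---|
| 1 | 0.461–0.697 | 0.485–0.757 |
| 1.5 | 0.686–1.009 | 0.707–1.009 |
| 2 | 0.817–1.009 | 0.832–1.009 |

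The value 1.009 arises where ρk = 1, for example k = 2 and ρ = 0.5.

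**KOOS JR. power.** Noncentral t, 112 df, one-sided 0.025, 57 per arm, noncentrality (14 − deficit) / (SD × √ratio × √(2/57)). For SD 20 and no deficit, unadjusted, this is 14 / (20 × 0.1873) = 3.737.

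| Assumed AUC/time SD | True deficit | Unadjusted | Ratio 0.82 | Ratio 0.69 | Ratio 1.01 |
|---|---|---|---|---|---|
| 15 | 0 | 99.9% | >99.9% | >99.9% | 99.8% |
| 20 | 0 | 95.9% | 98.3% | 99.4% | 95.8% |
| 25 | 0 | 84.2% | 90.5% | 94.6% | 83.9% |
| 15 | 5 | 88.8% | 93.9% | 96.9% | 88.5% |
| 20 | 5 | 66.3% | 74.9% | 81.8% | 65.9% |

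**Validity.** In simulations with 57 per arm, equal SDs, inter-visit correlation 0.6 and baseline correlation 0.2 to 0.6 (20,000 runs each), one-sided type I error was 0.023 to 0.028 unadjusted and about 0.026 for ANCOVA, with no bias in the unadjusted difference.

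**The case against.** The unadjusted t-test is a valid, prespecified choice that agrees with Protocol 10.4.2, so ANCOVA can look like mere preference. That it is no error is accepted; the case rests on precision alone.

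The size rests wholly on assumed SDs and correlations, and the gain can be nil. This stands. With SD ratio 1.5 and correlation 0.5 to 0.7, the KOOS JR. ratio is 0.95 to 1.01.

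The SD 25 row may also be too wide for the instrument. Patients spread evenly over the 29 raw scores in SAP Appendix 1 would have an SD of about 24.5, yet SD 25 with ratio 0.69 needs a per-visit post-operative SD of about 26 (k = 1.5, ρ = 0.1), and with ratio 0.82 about 28 to 30. This stands in part: those pairings are strained. With equal SDs and baseline correlation 0.1, however, an AUC/time SD of 25 needs a per-visit SD of only about 21, and the ratio is then 0.46, a larger gain.

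The most serious objection is timing. The study is unblinded. SAP 8.2 already reports many missing responses on one KOOS JR. item, and Protocol 10.4.2 plans an internal look at the secondary endpoints at soft lock. Changing the formal test after seeing outcomes would cost credibility. The SAP text shows knowledge of collected data, not that results by arm had been seen. The objection limits which form of the fix can be used, but it does not remove the point.

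**Conclusion.** The concern holds as a loss of efficiency, not as an error. Apart from one degree of freedom, ANCOVA on the Screening value cannot be less precise than the planned comparison, whatever fixed weight the AUC carries. Under the assumptions shown, its variance is 0.46 to 1.01 times the unadjusted variance, so the confidence interval is from about 32% narrower (√0.46 = 0.68) to about 0.5% wider (√1.01 = 1.005).

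For KOOS JR. the gain is useful if the AUC/time SD is large or iovera is truly somewhat worse, and negligible if the SD is moderate and the true difference is zero. The coefficients 0.964 and 0.833 depend on Baseline at Day 0 and nominal visit days; the direction of the conclusion does not. The power figures assume complete data. The change is worth making because the potential gain is material and the worst-case loss is under 1% of variance.

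**What to change.** Amend SAP 5.2 and 8.2 so that each secondary AUC/time endpoint is analysed by ANCOVA with treatment and that endpoint's own pre-randomisation baseline.

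- **KOOS JR.:** take the adjusted treatment difference and its standard error from each imputed dataset, combine them with PROC MIANALYZE, and test the same null hypothesis (Standard of Care minus Active at least 14) at one-sided 0.025. Margin, alpha, imputation scope and testing order stay as they are.
- **NRS and TUG:** ANCOVA on the data as now specified, without imputation and without a margin.
- **Baseline:** SAP 5.8 allows a fallback "If the value for an assessment is missing at Screening and there is an unscheduled assessment prior to treatment". Under SAP 3.2, "prior to study treatment, subjects will be randomized in a 1:1 manner", so such a value may fall after randomisation in an unblinded study. Limit the fallback to values taken before randomisation.
- **Disclosure:** list the change in SAP 3.5 and state whether outcome data had been seen. If they had, keep the protocol's t-test as the formal test and label ANCOVA a sensitivity analysis.

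The cost is one degree of freedom (1/110, about 0.9% of variance) and a disclosed departure from the protocol. Screening values are already collected, so patients carry no added burden.

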### **5.3 Handling of Dropouts and Missing Data**

Missing data for the primary effectiveness endpoint and the first secondary effectiveness endpoint will be imputed using multiple imputation methods. First, the relatively uncommon, non-monotone missing data will be imputed using the MCMC option of SAS® PROC MI. For example, for the primary effectiveness endpoint, the imputation model will include a term for treatment and the pill counts at visits 4, 5, and 6. Second, the monotone missing values will be imputed using the chained equation method by SAS® PROC MI option MONOTONE REG. For each subject within each imputed dataset, the value of the endpoint will then be determined. The imputed data sets will each be analyzed as specified in Sections 8.1 and 8.2, and the results will be summarized using PROC MIANALYZE.

### **5.4 Interim Analysis**

The analyses addressed in this SAP will utilize the final, locked database.

### **5.5 Multicenter Study**

This is a single site study.

### **5.6 Multiple Comparisons / Multiplicity**

The fixed sequential testing procedure will be used for the comparison of the two treatments with respect to the first (and key) secondary effectiveness endpoint. Therefore, for this endpoint, the analysis comparing the two treatments will be formally conducted only if the analysis for the primary effectiveness endpoint yields a statistically significant result. For informational purposes, however, the results of the analyses (i.e., p-value) will be presented regardless of the results for the primary effectiveness endpoint.

No adjustments for multiplicity will be made in the analyses.

## **5.7 Examination of Subgroups**

No subgroup analyses are planned.

## **5.8 Baseline**

Baseline will be defined as the value at the Screening visit. If the value for an assessment is missing at Screening and there is an unscheduled assessment prior to treatment, the value from the unscheduled assessment will be used as the baseline value.

## **5.9 Analysis Windows**

All analyses will be based on nominal visits.

## **6.0 ANALYSIS POPULATIONS**

### **6.1 ITT (Intent-to-Treat) Population**

All subjects who are randomized will be included in the ITT Population. In analyses based on the ITT Population, subjects will be analyzed according to the treatment group to which they were randomized. The primary analyses of effectiveness will be conducted based on the ITT Population.

### **6.2 Per Protocol Population**

The Per-Protocol Population is defined as the group of subjects who are randomized, who receive the treatment to which they were randomly assigned, and who complete their 6-week visit without any major protocol deviations. Receipt of an incorrect prescription will be considered as a major deviation; the definition of an incorrect prescription also includes deviations due to patients not taking Tramadol. In analyses based on the Per-Protocol Population, subjects will be analyzed according to the treatment group to which they were randomized. Analyses based on the PP population will be considered secondary analyses of effectiveness.

### **6.3 Safety Population**

All subjects who receive study treatment will be included in the Safety Population. Subjects will be analyzed according to the treatment they actually receive, regardless of their randomized treatment. All safety analyses will be based on the Safety Population.

